#### **4.2.1.5 Temperature**

Using the scheduled protocol assessments from the last assessment on Day 0 to quarantine discharge (including any extended quarantine period), this endpoint corresponds to the highest tympanic temperature.

#### **4.2.2 Safety**

The safety and tolerability will be evaluated by the monitoring of the occurrence of AEs and SAEs, clinical laboratory results, physical examinations, vital signs, electrocardiogram and concomitant medications.

##### **4.2.2.1 Adverse events**

Adverse events (AE) will be coded using the latest available version of the Medical Dictionary for Regulatory Activities (MedDRA) and will be classified by MedDRA Preferred Term (PT) and System Organ Class (SOC).

A Treatment Emergent Adverse Events (TEAE) will be defined as any adverse event that occurs from the time of first study treatment dose administered to the subject until last study visit, i.e. an AE that was not present prior to receiving the first dose of IMP.

Serious adverse events (SAE) are those AE that put the life of the subject at risk or that cause serious or permanent damage to the subject's health. An AE is to be recorded and reported as SAE in the event of any of the following:

- AE results in death
- AE is life-threatening (i.e. constitutes an immediate threat to the subject's life)

## Statistical Analysis Plan

- AE results in hospitalization of the trial participant or prolongs an existing hospitalization
- AE results in persistent or significant disability or incapacity
- AE is a congenital anomaly or birth defect.
- AE is another medically important condition: to be completed

Tolerability/safety will be assessed over the whole study period.

- Objective 8:
  - Frequency and severity of Adverse Events (AEs) and serious AEs (SAEs)
  - Frequency and severity of Treatment Emergent Adverse Events (AEs) and serious AEs (SAEs) Frequency and severity of drug related Treatment Emergent Adverse Events (AEs) and serious AEs (SAEs)

### 4.2.2.2 Laboratory endpoints

The following clinical laboratory tests are to be performed on collected blood samples:

- Clinical chemistry: Sodium, Potassium, Glucose (random), Albumin, Chloride, Bicarbonate, Calcium, Uric acid, Total protein, Creatinine, Total, direct, and indirect bilirubin, Inorganic phosphate, Blood urea nitrogen, C-reactive protein (CRP), Gamma glutamyl transferase, Alkaline phosphatase (ALP), Alanine transaminase (ALT), Lactate dehydrogenase (LDH), Aspartate transaminase (AST), Urea
- Hematology: Platelet Count, White blood cell (WBC) count (absolute), WBC differential (Neutrophils, Lymphocyte, Monocytes, Eosinophils, Basophils), Red blood cell (RBC) count, Reticulocyte count (% and absolute), Haemoglobin, Haematocrit, Mean corpuscular volume (MCV), Mean corpuscular haemoglobin (MCH), MCH concentration (MCHC).
- Coagulation: Prothrombin Time (PT), Activated Partial Thromboplastin Time (APTT)
- Cardiac enzymes: Creatine Kinase (CK), CK-MB, Troponin (T) Urinalysis: Colour, Specific gravity, Appearance, pH, Presence of blood, glucose, leukocytes, ketones, nitrites, proteins, urobilinogen, bilirubin by dipstick, Microscopy, culture and sensitivity examination (If the dipstick yields abnormal results)

### 4.2.2.3 Other safety endpoints

#### 4.2.2.3.1 Physical examinations

A complete physical examination to include a full systemic assessment will be performed (General Appearance, Eyes, Ears, Nose, Throat, Head & Neck, Cranial Nerves/ Nervous System, Musculoskeletal Skin, Cardiovascular (heart sounds, pulses), Abdomen/GI system, Respiratory System (breath sounds, resonance, added sounds), Chest – Auscultation (breath sounds, crepitations, wheeze, pleural rub), Chest – Vocal Resonance, Chest – Percussion, Other Findings)

Directed physical examinations will be conducted as deemed appropriate by the Investigator and will include examination of the ears, nose, throat and chest (via stethoscope).

Assessment and grading of any upper respiratory tract (URT) (nasal discharge, otitis, pharyngitis, sinus tenderness) and lower respiratory tract (LRT) symptoms (abnormal breath sounds externally [e.g. stridor] and on chest auscultation [wheezing or rhonchi, crepitations] will be performed. Physician-reported assessments of viral challenge related illness will be graded in accordance with their intensity and documented in the source data.

 Venn Life Sciences <small>Think Research</small>	Document Number or Project Identification: VH0001 / MB05-P-01-20
	Document Version: v3
Statistical Analysis Plan	

Safety will be assessed based on abnormalities (normal, abnormal NCS, abnormal CS) for complete examination, and on grades for directed physical examination.

#### **4.2.2.3.2 Vital signs**

The following vital signs will be performed:

- Weight (kg), Height (m/cm), BMI
- Heart rate (HR) will be recorded in beats per minute.
- Respiratory rate (RR): respirations will be counted and recorded as breaths per minute.
- BP: systolic BP and diastolic BP will be measured in millimeters of mercury (mmHg); measurements will be made supine.
- Peripheral arterial oxygen saturation (SpO2%) will be assessed using pulse oximetry
- Tympanic temperature (Celsius)

#### **4.2.2.3.3 Electrocardiograms (ECG)**

Twelve-lead ECGs will be obtained to evaluate the electrical activity of the heart.

#### **4.2.2.3.4 Concomitant medications**

Safety will also be assessed based on the analysis of Concomitant medications coded according to the latest available version of the WHO-Drug dictionary.

"Concomitant" is defined as a medication which was taken during treatment, e.g. stop date later than randomization.

All others will be considered "Prior".

#### **4.2.2.3.5 ADA**

- Objective 10:
  - Anti-Palivizumab antibody (ADA) through Day 28

#### **4.2.3 Pharmacokinetic endpoints**

- Objective 9:
  - Palivizumab serum concentrations and serum PK parameters through study Day +28
  - Nasal concentrations (if done) and serum PK parameters through study Day +28

#### **4.2.4 Other endpoints – Tertiary/Exploratory**

- Objective 12:
  - Assessments of spirometry, Peak Expiratory Flow (PEF), and Forced Oscillation Technique (FOT)
- Objective 13:
  - The average amount of instrument-assessed change for all participants who rate themselves as "a little better" or "somewhat better"

## **5 Statistical and Analytical Methods**

### **5.1 General statistical considerations**

The statistical analyses are performed in accordance with the ICH E9 guideline.

 Venn Life Sciences <small>Think Research</small>	Document Number or Project Identification: VH0001 / MB05-P-01-20
	Document Version: v3
Statistical Analysis Plan	

The statistical analyses will be performed by an external Contract Research Organisation (CRO), Venn Life Sciences, under the responsibility of the Sponsor.

### 5.1.1 Presentation of results

The following descriptive statistics will be presented:

- For quantitative variables: number of available values (N), number of missing values, mean (Mean), standard deviation (SD), CV (Coefficient Variation), median (Median), Q1 (or first quartiles), Q3 (third quartiles), minimum (Min), maximum (Max) values. When relevant, confidence intervals will be calculated for the mean (Student CI) or the median (Hahn & Meeker 1991).
- For qualitative variables: number of available values, number of missing values, number and percentage of observations in each category of the variable. Except if otherwise specified, percentages will be calculated using the number of available values as denominator (i.e., not including missing values). When relevant, confidence intervals of proportions will be calculated using the Clopper-Pearson exact method (Clopper & Pearson 1934).

All listing will be sorted by treatment group, subject number and time point if applicable.

### 5.1.2 Significance testing and estimation

When precised in section 5.3, between group comparisons will be performed using appropriate two-sided hypothesis tests at the 5% two-sided significance level.

For normally distributed continuous variables (either raw variable or log-transformed variables) the difference in means, the standard error and the 95% two-sided confidence interval (CI) will be presented. In case of log-transformed variables, in addition to the previous statistics on the log-transformed data, the geometric means and geometric mean ratio and its 95% two-sided CI for the original variable will be presented. The t-test, or Mixed Model for Repeated measures (MMRM) will be used, depending on the endpoint. For endpoints that are not normally distributed (such as total symptom scores), the Wilcoxon Rank-Sum test will be used.

The underlying assumptions of the MMRM presented in Section 5.4.2 will be checked by reviewing the standardized residuals ('Pearson') of the model. If necessary, splines (random coefficient linear regression spline) models will be computed and their fit compared with the fit of the linear model using AICs to address potential departure from linearity.

The underlying assumptions of the t-test will be checked by reviewing the distribution graphically and by reviewing the skewness, the kurtosis and the Shapiro-Wilks test.

For categorical variables, differences in absolute frequency and/or relative risks will be presented, with their 95% two-sided CIs will be presented. Except otherwise specified, the Chi-square test will be used to compare frequencies between groups.

P-values between 0.05 and 0.10 will be considered as indicative of a trend.

As the study is explorative by nature, there will be no attempt to adjust for the multiplicity of endpoints.

 Venn Life Sciences <small>Think Research</small>	Document Number or Project Identification: VH0001 / MB05-P-01-20
	Document Version: v3
Statistical Analysis Plan	

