#### 4.1.2. Part 2 design

Participants in Part 2 will be pre-screened for susceptibility to RSV infection, i.e., have levels of RSV neutralising antibodies compatible with susceptibility to RSV infection (the cut-off is based on the average 25th percentile of the past 12 months screening results).

Participants in Part 2 will be randomised to receive the following on Day -1:

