# 8.14. Nasal Discharge Collection from Paper Tissues

Each participant will be given pre-weighed packets of paper tissues. Participants will be asked to place single tissues used for nose blowing or sneezing into a specified bag (for that participant only).

A daily 24-hour collection will take place throughout the quarantine period. Distribution of paper tissues and bags will start on Day -2, with the first collection on Day -1. Thereafter distribution and collection of tissues will occur at 08:00h (± 1 hour). Tissues will be handed out daily and collection will occur until the discharge from quarantine.

In the event of a participant staying in quarantine beyond the planned day of discharge, the 24-hour distribution and collection of tissues and bags will continue until the participant is finally discharged from quarantine.

24-hour paper tissue collections will be analysed to determine the following over the quarantine period:

- 24-hour nasal discharge weight.
- The number of paper tissue used for nasal discharge over 24-hour period.

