#### 9.6.2.2. Inferential statistics and significance testing

Between group comparisons will be performed using appropriate two-sided hypothesis tests at the 5% two-sided significance level.

For normally distributed continuous variables (either raw variable or log-transformed variables) the difference in means, the standard error and the 95% two-sided confidence interval (CI) will be presented. In case of log-transformed variables, in addition to the previous statistics on the log-transformed data, the geometric means and geometric mean ratio and its 95% two-sided CI for the original variable will be presented. The t-test, analysis of covariance, or linear mixed-models for repeated measures will be used, depending on the endpoint. For endpoints that are not normally distributed (such as total symptom scores), the Wilcoxon Rank-Sum test will be used. Details on the method used for each endpoint will be provided in

the SAP. Methods for checking statistical model assumptions and alternative methods of analysis if the assumptions are not fulfilled will be described in the SAP.

For categorical variables, differences in absolute frequency and/or relative risks will be presented, with their 95% two-sided CIs will be presented. Except otherwise specified in the SAP, the Chi-square test will be used to compare frequencies between groups.

As the study is explorative by nature, there will be no attempt to adjust for the multiplicity of endpoints.

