# 9.6.7. Efficacy Endpoint(s)

Endpoints			Planned Inferential Analysis		
Area under the viral load-time curve (VL-AUC) of RSV-A Memphis 37b as determined by qRT-PCR on nasal samples collected twice daily starting two days post-viral challenge (Day +2) up to the end of quarantine.	t-test valid	if	assumptions		
Area under the viral load-time curve (VL-AUC) of RSV-A Memphis 37b as determined by cell culture on nasal samples collected twice daily starting two days post-viral challenge (Day +2) up to the end of quarantine.					
Area under the total symptom score-time curve (TSS-AUC) collected daily in the participant symptom diary card starting one day post-viral challenge (Day +1) up to the end of quarantine.					

Endpoints	Planned Inferential Analysis
Sum Total symptom score-time curve (TSS-Sum) collected daily in the participant symptom diary card starting one day post-viral challenge (Day +1) up to the end of quarantine.	MMRM for repeated measures, if underlying assumptions valid
Total weight of nasal discharge produced starting one day post viral challenge (Day +1) up to the end of quarantine.	t-test if assumptions valid
Total number of tissues used by participants starting one day post viral challenge (Day +1) up to the end of quarantine.	
Occurrence of at least two positive "quantifiable" qRT PCR measurements in nasal samples at different timepoints reported within two or more consecutive days starting two days post viral challenge (Day +2) up to the end of quarantine.	Chi-square test
Occurrence of at least two positive "detectable" qRT PCR measurements in nasal samples at different timepoints reported within two or more consecutive days starting two days post viral challenge (Day +2) up to the end of quarantine	
Number of days with quantifiable qRT PCR measurements in nasal samples starting two days post viral challenge (Day +2) up to the end of quarantine.	t-test if assumptions valid
Peak viral load of RSV-A Memphis 37b as defined by the maximum viral load determined by quantifiable qRT PCR measurements in nasal samples starting two days post viral challenge (Day +2) up to the end of quarantine.	t-test if assumptions valid
Incidence of symptomatic RSV infection, as defined by:  o Incidence of infection, and	Chi-square test (on both the composite and each component)
o At least one grade 2 symptom from one or more respiratory categories from the participant symptom diary card.	

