## 5.4 Efficacy analyses

### 5.4.1 Primary efficacy analysis

#### **Objective 1:**

To estimate the margin and variance of prophylactic effect of Intravenous (IV) treatment with Palivizumab administered 1 day prior to inoculation in the RSV human challenge model in healthy

 Venn Life Sciences Think Research	Document Number or Project Identification: VH0001 / MB05-P-01-20
	Document Version: v3
Statistical Analysis Plan	

adults compared to Placebo [assessed by quantitative reverse transcriptase-polymerase chain reaction (qRT-PCR)].

Area under the viral load-time curve (VL-AUC) of RSV-A Memphis 37b as determined by **qRT-PCR** on nasal samples collected twice daily starting two days post-viral challenge (Day +2) up to the end of quarantine will be calculated (using the trapezium rule) and tabulated per treatment group. Treatment groups will be compared using t-test if assumptions are valid (Statistical Table 14.2.1.1). In case of distribution not normal, a data transformation could be used.

qRT-PCR will be also tabulated per visit/timepoint for each treatment group (Statistical Table 14.2.1.2).

Spaghetti plots and mean value over time will be used for graphical presentation of qRT-PCR, boxplot will be used for AUC presentation (Statistical Figures 14.2.1.1 to 14.2.1.3).

Individual data for qRT-PCR (included derived data) will be presented on Listing 16.2.6.1.

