#### **5.4.2.2 Symptoms evaluation**

##### **a) Objective 3:**

To estimate the margin and variance of prophylactic effect of IV treatment with Palivizumab administered 1 day prior to inoculation in the RSV human challenge model in healthy adults compared to Placebo [assessed by total symptom score (TSS)].

A total symptom score will be derived for each subject, separately for each assessment (symptom diary card) on each day, as the sum of the 13 observed symptom grade values for each symptom diary card to obtain a total symptom score for each symptom diary card. If the subject does not have all 13 observed values on a specific symptom diary card being considered, then total symptom score will not be calculated for that symptom diary card. It is expected that subjects will not have missing data.

 Venn Life Sciences <small>Think Research</small>	Document Number or Project Identification: VH0001 / MB05-P-01-20
	Document Version: v3
Statistical Analysis Plan	

Area under the total symptom score-time curve (TSS-AUC) collected daily in the participant symptom diary card starting one day post-viral challenge (Day +1) up to the end of quarantine will be calculated (using the trapezium rule) and tabulated per treatment group. Treatment groups will be compared using t-test if assumptions are valid (Statistical Table 14.2.5.1). In case of distribution not normal, a data transformation could be used.

The TSS will be also tabulated per visit/timepoint for each treatment group (Statistical Table 14.2.5.2). Spaghetti plots and mean value over time will be used for graphical presentation of TSS, boxplot will be used for AUC presentation (Statistical Figures 14.1.4.1 to 14.1.4.3).

Following tables will also be displayed:

- Qualitative description for each symptom per visit/timepoint and treatment group (Statistical Table 14.2.5.3)
- Quantitative description (in mm) for each symptom per visit/timepoint and treatment group (Statistical Table 14.2.5.4)

Individual data for Symptom diary cards (included data) will be presented on Listing 16.2.6.3.

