**b) Objective 4:**

To estimate the margin and variance of prophylactic effect of IV treatment with Palivizumab administered 1 day prior to inoculation in the RSV human challenge model in healthy adults compared to Placebo [assessed by total symptom score (TSS)].

Sum Total symptom score-time curve (TSS-Sum) collected daily in the participant symptom diary card starting one day post-viral challenge (Day +1) up to the end of quarantine will be analysed using a MMRM if underlying assumptions valid (Statistical Table 14.2.5.5).

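### Continuous efficacy endpoints are compared with no baseline covariate although pre-dose titre, symptom and tissue data are already collected: a missed, probably modest, precision gain

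*SAP*

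**What the plan says.** **General methods.** Protocol 9.6.2.2 reads "The t-test, analysis of covariance, or linear mixed-models for repeated measures will be used, depending on the endpoint" and leaves the method for each endpoint to the SAP. The matching sentence in SAP 5.1.2 reads "The t-test, or Mixed Model for Repeated measures (MMRM) will be used, depending on the endpoint".

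**Endpoint level.** The table in Protocol 9.6.7 uses entries such as "t-test if assumptions valid", with an MMRM for TSS-Sum and chi-square tests for incidence. It assigns ANCOVA to no endpoint. SAP 5.4.1 and 5.4.2 follow it: two-sample t-tests, with a possible transformation, for VL-AUC (qRT-PCR and culture), TSS-AUC, peak viral load, peak symptom score, numbers of days, and discharge weight and tissue count. No covariate is named. The TSS-Sum MMRM in SAP 5.4.2.2 has no stated fixed effects, covariates or covariance structure.

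**Baseline data.** Part 2 participants must "have levels of RSV neutralising antibodies compatible with susceptibility to RSV infection" (Protocol 4.1.2). The Part 2 schedule takes serum for the neutralisation assay at screening and on Day -3 or -2. It shows a symptom diary card on Day -3 and three a day from Day -2. On tissues, Protocol 8.14 says "Distribution of paper tissues and bags will start on Day -2, with the first collection on Day -1". Dosing is on Day -1 and challenge on Day 0. SAP 5.2.1.1 defines baseline as the last non-missing value before dosing.

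**Use of baseline immunity.** The SAP uses the titre for seroconversion and, under Objective 13, as an optional exploration with no model and no table (SAP 5.4.3).

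**The concern.** Part 2 exists to estimate the size and variance of the palivizumab effect so that later biosimilar studies can be planned (Protocol 2.2). There are 25 participants per arm, and the planning CV for VL-AUC is 87.9%. In that setting a prognostic baseline variable can tighten the estimate without any new data.

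Three candidates are already in the schedule. The protocol treats neutralising antibody as relevant to susceptibility. A participant's own background symptoms and habitual tissue use could plausibly predict later values of the same measures. Randomisation is 1:1 with no stratification factor stated, so any of these may be unbalanced by chance. The unadjusted analysis leaves that imbalance in the point estimate and carries the explainable variation in its standard error.

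**Working it through.** **1. Reproduce the planned figure.** Inputs from Protocol 9.2.2: placebo mean VL-AUC 20.3, SD 17.8, 70% reduction, two-sided 5%, 80% power, 25 per arm.

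- Difference = 0.70 × 20.3 = 14.21.
- n per arm = 2 × (1.960 + 0.842)² × 17.8² / 14.21² = 24.6, rounded up to 25, as stated. The other six entries in the N/group row also reproduce (49, 40, 34, 29, 22, 19).
- Standard error = 17.8 × √(2/25) = 5.035. Power = Φ(14.21/5.035 − 1.960) = Φ(0.862) = 0.806, against 0.800 stated (0.790 by noncentral t).
- 95% CI half-width = 2.011 × 5.035 = 10.12.

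The sample size therefore rests on an unadjusted two-sample comparison.

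**2. Size of chance imbalance.** The difference in arm means of any baseline variable has standard error √(2/25) = 0.283 SD, so a gap of at least 0.4 SD arises about 16% of the time. At an assumed correlation of 0.3, a 0.4 SD gap moves the VL-AUC difference by 0.3 × 0.4 × 17.8 = 2.1, or 15% of 14.21.

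**3. Effect of one covariate.** Let r be the within-arm correlation of covariate and outcome. It is not in the documents, so a range is shown. With the slope estimated from N = 50 and a roughly normal covariate:

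- Variance factor = (1 − r²) × (1 + 1/(N − 4)) = (1 − r²) × 1.0217.
- Equivalent n per arm = 25 / factor.
- Half-width = 2.012 × 5.035 × √factor.
- Power = Φ(2.822/√factor − 1.960), for a 70% reduction.

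| r (assumed) | Factor | Change in variance | Equivalent n per arm | VL-AUC half-width | Power |
|---|---|---|---|---|---|
| none (current plan) | 1 | 0 | 25 | 10.12 | 0.806 |
| 0.1 | 1.012 | about +1% | 24.7 | 10.19 | 0.801 |
| 0.15 | 0.999 | about 0% | 25.0 | 10.12 | 0.806 |
| 0.2 | 0.981 | −2% | 25.5 | 10.03 | 0.813 |
| 0.3 | 0.930 | −7% | 26.9 | 9.77 | 0.833 |
| 0.5 | 0.766 | −23% | 32.6 | 8.87 | 0.897 |

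Break-even is where 1 − r² = 1/1.0217, so r² = 0.0213 and r is about 0.15. The last two columns apply to VL-AUC only, since the documents give no SD for the symptom or discharge endpoints.

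**4. How large r could be for titre.** Protocol 4.1.2 bases the entry cut-off on the 25th percentile of screening results. If entrants were the lowest quarter of a normal log-titre (assumption), the covariate SD would shrink by a factor u = 0.49. By r·u/√(1 − r² + r²u²), an unrestricted 0.3 becomes about 0.15 and 0.5 becomes about 0.27. SAP 5.2.3.2 narrows the spread further: titres from 10 to below 156 are all set to 156/2 = 78, and no detectable antibody is set to 10.

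**The case against.** The strongest reply is that nothing is wrong with the plan. Under 1:1 randomisation the unadjusted difference is unbiased, and its confidence interval already allows for chance imbalance. The sample size uses the unadjusted SD, and raw arm means and SDs are what a later study would need. All of that stands; an adjusted residual SD is a different quantity and must not replace the raw one.

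A reader might infer that the SAP removed a planned ANCOVA and failed to record it in SAP Section 8. The documents do not support this. The protocol's endpoint table never assigned ANCOVA, and Protocol 9.6.2.2 leaves the method for each endpoint to the SAP.

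Nor is every continuous endpoint compared by t-test. TSS-Sum has an MMRM, shedding duration uses Kaplan-Meier, time to peak is descriptive, and SAP 5.1.2 names the Wilcoxon test for non-normal endpoints. Because the MMRM terms are not given, it cannot be called unadjusted either.

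The gain is also unproven. For titre, range restriction may take r to break-even. For symptoms and tissues, entrants are healthy and those with recent respiratory infection or clinically active rhinitis are excluded, so pre-dose values may sit near zero and r = 0.5 may be optimistic. These points limit the benefit. They do not remove the case for a prespecified pre-dose covariate where one is available at almost no cost.

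**Conclusion.** The point holds as a missed precision gain. It is not an error, a bias or a protocol deviation. SAP 5.4 names no covariate for its t-test comparisons and no terms for its MMRM, although suitable baseline measures are already scheduled.

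Its size depends on a correlation that the documents do not give. Over the assumed range 0.15 to 0.5, the variance of the comparison changes by about 0% to −23%. For the primary VL-AUC endpoint adjusted for titre, the low end is more likely. It would be tempting to quote the figure at r = 0.5 as the expected benefit, but nothing in the documents supports that value. Below about r = 0.15 adjustment costs a little precision. The calculation assumes 25 per arm, one covariate and a roughly normal covariate; the titre, with its substituted values, may depart from the last of these.

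**What to change.** Amend SAP 5.1.2 and 5.4 to prespecify a linear model with treatment plus one pre-dose covariate per endpoint family:

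- **Viral endpoints:** log RSV neutralising titre from the Day -3/-2 sample.
- **Symptom endpoints:** mean TSS over diary cards completed before dosing, also entered as a term in the TSS-Sum MMRM, whose remaining terms and covariance structure should be written out.
- **Discharge endpoints:** the 24-hour tissue weight or count collected on Day -1, provided that collection closes before dosing.

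Use nothing from after the Day -1 dose. That rules out Day 0 pre-challenge diary and tissue values and the optional Day 0 serum sample, and keeps the covariates consistent with SAP 5.2.1.1. Confirm which diary cards exist before dosing: the schedule shows three a day from Day -2, but its notes say three-times-daily assessments start on Day 0.

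Report the unadjusted difference and raw arm SDs alongside, because variance is a study output. Baseline titre could also be tabulated by arm, as it is missing from the list in SAP 5.3.3.

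Cost: SAP wording, one degree of freedom, no new data, and a variance increase of about 1% if r is only 0.1.
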